3.2.1 Primary outcomes

Primary outcomes will be the change in bacterial load compared to baseline. (see appendix A – molecular microbiology protocol for details on quantification). [name] laboratory at UM Miller School of Medicine, Department of Dermatology and Cutaneous Surgery will be the coordinating center responsible for tissue sample receipt and

processing. Bacterial load in CFU/g among treatment and control arms will be calculated for each wound at visits T0, T2 and T3. The trajectories of bacterial load for each subjects and average change in bacterial load between groups will be compared.

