5.16 Tissue collection

Tissue collection will be conducted at visits T0, T2 and T3 as per appendix A. All collection containers are pre-labeled with the subject ID. After collection, the date is written on the container label.

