5.21 Instructions for follow up care

Once subjects are identified as healed, they will move into the follow up phase. Subjects who completed the treatment phase (regardless of healing status) will be moved to the follow up stage as well. While in the follow up phase, subjects will be returned to the care provider who referred them to the study and follow up care will consist of appropriate compression therapy, wound care (if needed) and other medically indicated treatments as determined by the PI.

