Prior to performing statistical analyses on quantitative study data, the data will be checked, screened and verified to ensure the integrity of the database. Data screening will focus on several aspects. We will determine the amount, the pattern, and randomness of missing data. We will define outliers as observations that appear to be very high or very low, and decide how to proceed based on the presumed cause. We will identify inconsistencies within a single variable and between variables. Initially, we will perform an explanatory data analysis; visually via graphics/plots and numerically by descriptive statistics with mean, standard deviation for measurements taken on a continuous scale, and frequencies and percentages, various types of cross-tabulations for measurements taken on a categorical scale. Corresponding confidence intervals (CI) for means and proportions will be calculated. To have a better understanding of the relationships among different study measurements, parametric or non-parametric correlation coefficients, bivariate/multidimensional cross-tabulations will be constructed. All the descriptive statistics will be reported for all subjects and by study arm.

The primary endpoint of the study, the bacterial load in CFU/g, will be calculated for each wound at visits T0, T2 and T3 among Study Device and Comparator arms. The difference in means of the bacterial load from T3 to T0 will be calculated and compared between study arms with Student's t-test. To be able to study the trajectories of the bacterial load over time, overall and by study arms, the time series plots will be depicted and repeated measures regression analysis will be performed where time and study arm as the main effects. Types of variance-covariance matrix will be determined by standard statistical procedures. We plan to expand the regression model and include other subject characteristics for additional covariate adjustment. Adjusted regression coefficients and corresponding 95% confidence interval (95%CI) will be reported for the study arm as the main effect in the regression models.

The secondary endpoints such as microbiological outcomes, clinical wound outcomes, pain related outcomes, quality of life measurements, and safety outcomes will be analyzed with similar statistical methods as the primary endpoint.

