VLU debrided tissue will be collected from patients at the initial clinic visit (T0) and at routine follow-up visits (T2 and T3). Collected tissue will be measured and immediately after preserved at -80°C. DNA will be extracted from all samples using a solvent and grinding DNA extraction protocol (Bacterial/Fungal DNA isolation kit-Zymo Research). DNA quality and quantity control will be assessed by Real-Time PCR (qPCR) and Quant-It PicoGreen assay (Life Technologies), respectively. All of the methods required for DNA isolation and analysis are well established in [name] laboratory [32]; [33]; [34]. Quantification of all bacterial species in wound samples will be performed based on PCR amplification of 16S rRNA gene. The 16S rRNA gene (rDNA) is a DNA segment in all bacteria and archaea that codes for a structural RNA component of the small ribosomal subunit. The 16S rDNA is commonly used to quantify bacteria from human wound samples. We will employ 16S rDNA multiple hypervariable region to accomplish microbial quantification in VLU. Specifically, the 16S rDNA V1-V3 variable regions will be PCR

amplified to enrich the samples using the degenerate forward 27F.1 and non-degenerate reverse 518R primers that consist of sequences flanking the conserved hypervariable region. Separate PCR reactions will be prepared for each sample, including positive PCR control, and no template control. Real-time PCR will be performed and data will be analyzed using standard procedures established in [name] laboratory. Standard graphs will always be prepared from data accumulated at the same time as the test samples to act as internal controls. All qPCR reactions will be done in triplicate using the CFX96 real-time PCR system (Bio-Rad) and the PerfeCTa SYBR Green SuperMix (Quanta BioSciences). The relative CFUs will be calculated based on the standard curve. Assay results will be expressed as threshold cycle number (Ct) of the 16S rRNA gene copies per sample and tissue mass (mg). Standard curve will be used to determine relative CFUs based on Ct. Relative CFUs for tissue at two-weeks post initial treatment application (T2), and three weeks post treatment application (T3, if the percentage area reduction did not reach 75%). This qPCR based approach allows detection of bacteria which are difficult to cultivate and that would in all practicality remain undetected or underestimated by standard culture microbiology methods.

DNA standards for determining bacterial number by qPCR

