Escherichia coli DNA is generally used as the standard for determining bacterial number by qPCR. However, to minimize the effect of variations in rDNA copy number on the calculation of bacterial number, DNA standards will be also prepared from two common VLU isolates, *Staphylococcus aureus* and *Pseudomonas aeruginosa*.

Detection of genes for resistance to silver

Resistance to silver compounds as determined by bacterial plasmids and genes has been defined by molecular genetics. Plasmid pMG101 is a 180-kb silver resistance plasmid that also confers resistance to several antibiotics. The possibility of the horizontal transfer and the increasing use of silver for wound dressing has raised concerns that bacterial resistance to silver might proliferate in a manner analogous to that seen for antibiotics and thereby compromise its clinical utility. The sil operon comprises nine ORFs, seven of which are apparently structural genes (silE, silC, silF, silB, silA, ORF105 and silP) and two of which (silR and silS) encode a putative two-component regulatory circuit. To date, only the function of SilE, SilP and SilS has been determined. SilE, functions as a periplasmic silver-binding protein by restricting the accumulation of silver in the cell through a combination of silver sequestration in the periplasm. SilP is responsible for active efflux as an ATPase transporter, and SilS encodes a regulatory circuit. For detection of these three silver resistance genes, a PCR method will be used. DNA isolated from all tissue samples collected at all time points will be screened for the silE gene silP and silS genes. This PCR base approach allows for detection of silver resistance even in bacteria that may not be grown using standard microbiology approach. Detection of genes encoding for silver resistance will be performed in batches from DNA isolated from 2 samples and more. *E. coli* strain ATCC 25922 (with the complete sil gene cassette) will be included as a positive control. The agarose gel electrophoresis of PCR products for silS, silE, and silP genes will be employed to confirm the expected size of the amplicons.

The PCR products will be confirmed by sequencing and the sequence will be analyzed for homology with the sil genes from pMG101 (NCIB Accession number AG067954) and *E. cloacae* Ag703 (NCIB 679159).

Susceptibility determinations and selection/phenotypic characterization of silver-resistant strains

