qPCR Data will be analyzed using the software Prism (Graphpad, La Jolla, CA, USA). Raw data for qPCR will be provided to sponsor in txt format. All results including microbiology analyses, silver resistance and quantification of bacterial load will be presented in the final study report including analysis of data. PCR results will be expressed as threshold cycle number (Ct) of the 16S rRNA or silver resistance gene copies per sample and corresponding CFU/g tissue; the mean and standard deviation will be calculated for each time point. The longitudinal changes in bacterial load as

determined based on qPCR data analyses gene will be examined individually for each tissue. After counting the colonies for the MIC analyses, the data will be tabulated and the Log of colony forming units/g (Log CFU/g) determined. [name] will provide final results to include raw data.

CONFIDENTIAL

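### Appendix A makes the T3 bacterial load conditional on area reduction below 75%, against Sections 3.2.1 and 7; probably leftover text, but if followed it would remove some open wounds from the primary t-test

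*Combined protocol and SAP*

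**What the plan says.** Section 3.2.1 defines the primary data without any condition: "Bacterial load in CFU/g among treatment and control arms will be calculated for each wound at visits T0, T2 and T3". It sends the reader to Appendix A for how load is quantified. Section 7 repeats the three visits for each wound and sets the primary test: "The difference in means of the bacterial load from T3 to T0 will be calculated and compared between study arms with Student's t-test". Section 5.16 has "Tissue collection will be conducted at visits T0, T2 and T3 as per appendix A", and Table 1 schedules the same three collections.

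Appendix A, under DNA Isolation and qPCR, says "DNA will be extracted from all samples using a solvent and grinding DNA extraction protocol". Later in the same paragraph it lists the relative CFUs at T2 and then at "three weeks post treatment application (T3, if the percentage area reduction did not reach 75" per cent. Elsewhere Appendix A treats T3 without condition. The time-point definitions describe it only as three weeks after first application, the silver-resistance screen uses "DNA isolated from all tissue samples collected at all time points", and in the reporting section "the mean and standard deviation will be calculated for each time point".

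On healed wounds, Section 5.21 says "Once subjects are identified as healed, they will move into the follow up phase". On missing data, Section 7 plans to describe amount, pattern and randomness, but gives no rule for an absent T3 value.

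**The concern.** A wound without a T3 load cannot enter a t-test on T3 minus T0. Treatment ends early only on healing (Sections 3.1 and 5.21). A wound past 75% but still open is therefore still dressed and debrided at T3 and scheduled for sampling, and its DNA is extracted. If the Appendix A condition were applied, only its primary-endpoint value would be dropped.

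That would be selection on a post-randomisation result, because percent area reduction is itself a secondary outcome (Section 3.2.2). The protocol's own rationale links healing to bacterial load, so the wounds removed need not be typical in load change. Section 7 gives the pilot's purpose as producing effect estimates to size later studies, so it should be clear who contributes to the primary estimate.

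**Working it through.** **Text comparison.** Sections 3.2.1, 5.16 and 7, Table 1, and the collection, extraction, time-point and reporting text of Appendix A all treat T3 unconditionally. One sentence in Appendix A does not, and nothing repeats or explains it. That sentence has no main verb, names T2 and T3 but not T0, and does not say from which visit the 75% is counted or by which area method (Section 5.14 plans both ruler and imaging). The two readings cannot both govern the primary endpoint.

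**Inputs.** From the documents: 15 completers per arm (Section 4.1; 30 in total in Section 7) and alpha 0.05 (Section 7; two-sided is assumed). The 45 in the executive summary is a separate discrepancy and is not used here. The documents give no rate of passing 75%, healed share, SD or correlation. All of these are assumptions. Low rates are plausible, since ulcers changing by more than 30% before treatment are excluded (Section 4.3) and T3 is only three weeks in.

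**Precision.** The 95% half-width in SD units is t(0.975, n1+n2−2) × √(1/n1 + 1/n2). With everyone, 15 v 15, it is 0.748. Wounds healed before T3 are taken out of both sides of the comparison, because removing the condition does not recover them.

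- 1 v 2 wounds past 75%, of which 0 v 1 healed: 15 v 14 without the condition gives 0.762; 14 v 13 with it gives 0.793. Ratio 0.793/0.762 = 1.04.
- 2 v 4 past 75%, of which 1 v 2 healed: 14 v 13 gives 0.793; 13 v 11 gives 0.850. Ratio 0.850/0.793 = 1.07.

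**Bias.** Take load reduction and healing as jointly normal with SD 1 and correlation r. Removing the top share p of healers lowers the mean load reduction among those kept by r·φ(z)/(1−p), where z is the normal quantile of 1−p. The total uses p = share past 75%. The part that remains after the fix uses f·p, where f is the share of those already healed. Net bias is total minus remainder, as a difference between arms.

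Example at 10% v 30%, r = 0.5, f = 0.5:

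- Total: 0.5 × (0.497 − 0.195) = 0.151.
- Remainder, at 5% v 15%: 0.5 × (0.274 − 0.109) = 0.083.
- Net: 0.151 − 0.083 = 0.068.

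| Past 75% by arm | f | r | Net bias (SD) |
|---|---|---|---|
| 5% / 10% | 0.5 | 0.3, 0.5, 0.7 | 0.011, 0.019, 0.026 |
| 10% / 30% | 0.5 | 0.3, 0.5, 0.7 | 0.041, 0.068, 0.095 |
| 10% / 30% | 0.25 | 0.5 | 0.104 |
| 10% / 30% | 0.75 | 0.5 | 0.034 |

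Net bias is 0 at equal rates or zero correlation. At r = −0.5 it has the same size and the opposite sign. The largest half-healed value against the 14 v 13 half-width is 0.095/0.79 = 12%.

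**Open wounds without tissue.** Debridement removes only non-viable tissue (Section 5.17), so nearly closed wounds may yield none, and the fix cannot recover those either. Suppose half of the wounds past 75% are healed, and half of the open remainder, the most healed of them, yield nothing. The unrecoverable share is then 0.5 + 0.25 = 0.75, which is the last table row: net bias falls from 0.07 to about 0.03. The 4% and 7% widenings also shrink once such wounds are allowed for.

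**The case against.** The strongest reply is that the clause is not an operative rule. Read literally as a list of what is quantified, it would drop the baseline too, and no change score could exist. The sentences around it are unconditional. No reference visit or area method is given, and no section sends wound area to the blinded laboratory, whose containers carry subject ID and date. This largely stands and makes leftover text the probable explanation. It does not remove the need to correct the sentence: it sits in the text to which Sections 3.2.1 and 5.16 point for quantification and collection, so a laboratory could follow it.

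Two further replies also stand. The planned repeated-measures regression would still use T0 and T2 from the affected wounds, so their data are not wholly lost. The planned missing-data check would already show part of the problem.

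A reader might infer more than the documents support:

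- *That the primary analysis will lose wounds or is biased.* Nothing shows that the condition will be applied. Even if it is, the cost is zero when no open wound passes 75%.
- *That the bias has a known direction.* It runs against the better-healing arm only if faster healing goes with larger load reduction, and it reverses if the correlation is opposite.
- *That every wound past 75% is lost because of this clause.* Wounds healed before T3 move to follow-up in any case, so figures that count all wounds past 75% overstate its effect.

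**Conclusion.** The contradiction is in the current text and should be corrected, because one reading changes who enters the primary test. That much is certain. Whether the clause would ever be followed is not, and the signs point to leftover text.

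If it were followed, open wounds past 75% that yield tissue would leave the t-test. Some precision would then be lost. Bias would arise only if healing correlates with load change and the arms pass 75% at different rates. Under the assumed inputs the effect is modest at most: intervals about 4-7% wider, and net bias about 0.01-0.10 SD with half of the wounds past 75% healed. Both figures are before allowing for open wounds without tissue, which lowers them. The larger bias values need 10% v 30% of wounds past 75% within three weeks, for which the documents offer no support.

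The SD-unit figures assume a roughly normal change, as on a log10 scale. The plan does not fix that scale for the t-test: the endpoint is CFU/g, transformed only when indicated. This is a cheap correction worth making, not a flaw that undermines the trial.

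**What to change.** In Appendix A, delete the 75% condition and complete the sentence, for example: *Relative CFUs will be calculated at T0, T2 and T3 for every study ulcer that is still open and yields tissue.* This brings it into line with Sections 3.2.1 and 7.

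In Section 7, add one line to the planned missing-data check: report by arm the number of wounds without a T3 value and the reason (healed, no tissue, missed visit).

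The t-test stays primary, and the regression model needs no change. If the condition was in fact intended, it should be stated in Sections 3.2.1 and 7 with its reason and its handling in the analysis; the selection would then remain.

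The cost is two short edits and at most about 1 to 3 more T3 samples for triplicate qPCR: 15 × (0.05 + 0.10) × 0.5 = 1.1 at the lower rates and 15 × (0.10 + 0.30) × 0.5 = 3.0 at the higher, from tissue already scheduled for collection. Some T3 values will still be missing, because healed and nearly closed wounds may give no tissue.

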3.2.2 Secondary outcomes

Secondary outcomes will include:

Microbiological outcomes: bacterial silver resistance characterization on molecular and phenotypic level over time (see appendix A for molecular microbiology protocol).

Clinical wound outcomes: healing rate and percent reduction in area over 6 weeks will be calculated by measuring wound area at each visit and dividing the area change by 6 to calculate average wound healing rate in cm^2/week and the average percent reduction for each study arm.

Complete healing at 6 weeks – the proportion of subjects in each study arm in which the study ulcer achieved complete healing at visit F1.

Pain related outcomes: pain assessments will be collected at every visit using visual analog scale (VAS) and time from visit T0 to clinically meaningful decrease in pain (i.e. 33% reduction from baseline) [21] will be calculated. Additionally, time to first indication of no pain will be calculated (i.e. VAS < 5mm)

Quality of life measurements: the EQ-5D-5L [22] and the Wound Quality of Life (WQoL) [23, 24] instruments will be used and assessments take place at visits T0, T4 and F1.

Safety outcomes: adverse events will be recorded at every visit and type and frequency logged and compared between arms.

4. Study population

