This research protocol will provide information that may further the understanding of Cutimed® Sorbact® treatment in accelerating wound healing via changes in microbial load and prevention of silver resistance. The bacterial load is increased in non-healing

VLU and promoting a non-healing wound phenotype. We will also evaluate expression of specific set of silver resistance genes whose expression may be stimulated by prolonged Ag-based therapy. [14]

Tissue Collection Procedure

Debridement tissue samples will be taken from the edge of the wound and will be taken at the initial visit and 2 additional points during the trial. The tissue will be transported in a sterile container on ice to [name] lab immediately after collection. One half of the tissue will directly stored into -80°C freezer for DNA isolation; the second half will be preserved in 80% glycerol for colony isolation using standard microbiology and analyzes of silver resistance on phenotypic level. The initial tissue removed will be considered the baseline and will be noted as T0.

Time Point Definitions

T0 – Pre-Randomization

T2 – Two weeks post-initial application SOC+ Cutimed® Sorbact® or SOC + Acticoat®

T3 – Three weeks post-initial application SOC+ Cutimed® Sorbact® or SOC + Acticoat®

DNA Isolation and qPCR

High bacterial burden ($>10^5$ organisms per gram of tissue), even without the classic signs of infection, is detrimental to healing [1, 10, 29]. Bacteria are routinely isolated from VLU by culturing methods. However, standard microbiology techniques present barriers to accurate microflora quantification because many of the chronic wound bacteria are recalcitrant to growth in a culture and are therefore difficult to identify in this manner [30]; [31]; [1]. The availability of molecular PCR based methods has provided researchers with the capability to examine the bacterial composition of human tissue samples in unprecedented detail. This approach would be utilized to further our understanding of mechanism of action Cutimed® Sorbact® on bacterial populations in VLU.

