Once we determine samples positive for the silver resistance genes we will further investigate whether the bacteria possessing Ag-resistant genes express this trait phenotypically. Bacteria will be isolated from the preserved glycerol stocks using standard microbiological methods (culturing on selective media). Tissue samples will be evaluated for the bacterial growth using microbiology methods. Culture condition will include both anaerobic and aerobic growth to enhance the level of bacterial detection. To recover bacteria serial dilutions from preserved stocks will be made from all tissue samples. The extent of microbiological colonization will be assessed using the Spiral Plater System. All plates will be incubated both aerobically and anaerobically at 37°C, after which the number of viable colonies will be counted. After the incubation period, colonies on the plates will be enumerated and the CFU/mL calculated. Similar methods have been used in our laboratories to evaluate the antimicrobial efficacy of various topical agents [33, 34]. All isolates will be tested for growth on LB agar supplemented with 250 µM Ag+ using patch method. Further Ag resistant phenotype will be confirmed for individual isolates using minimal inhibitory concentration (MIC) method.

MIC test to determine susceptibility to silver nitrate

The MIC of silver nitrate will be determined for all isolates capable of growing on LB agar supplemented with 250 µM Ag+. Bacteria will be suspended in Iso-Sensitest broth (Oxoid Ltd., USA). After an overnight incubation at 37°C, 10 µl of the bacterial suspension will be inoculated into a series of tubes with increasing concentrations of silver nitrate (4 to 512 mg/liter) in the same broth. The final bacterial concentration will be 105 CFU/ml. After 24 h of incubation, the MIC will be recorded as the lowest concentration yielding no visible growth. A silver nitrate MIC of >512 mg/liter will classify the bacterium as silver resistant. *E. coli* strain ATCC 25922 will be used as a control. Isolates confirmed for silver resistance will be preserved and further identification of bacteria on a species specific level will be proposed to sponsor.

Data Analyses and Reporting

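### The silver-resistance gene result is described two ways in Appendix A, and neither relates it to the sample's 16S load, so a fall in bacterial load may be read as a fall in resistance

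*Combined protocol and SAP*

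**What the plan says.** Section 3.2.2 lists as a secondary outcome "bacterial silver resistance characterization on molecular and phenotypic level over time". The Rationale in Appendix A (9.1) treats load and resistance as two separate effects of the study dressing: "accelerating wound healing via changes in microbial load and prevention of silver resistance".

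Appendix A describes the gene measurement in two places.

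- **Detection of genes for resistance to silver:** "DNA isolated from all tissue samples collected at all time points will be screened for the silE gene silP and silS genes". The read-out is a gel followed by sequencing: "The agarose gel electrophoresis of PCR products for silS, silE, and silP genes will be employed to confirm the expected size of the amplicons". The next subsection uses the result as a yes/no status that leads into phenotypic testing: "Once we determine samples positive for the silver resistance genes we will further investigate".
- **Data Analyses and Reporting:** PCR results are expressed as "threshold cycle number (Ct) of the 16S rRNA or silver resistance gene copies per sample and corresponding CFU/g tissue", and "the mean and standard deviation will be calculated for each time point".

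Total load is measured by 16S qPCR on the same tissue samples (Appendix A, DNA Isolation and qPCR). Section 7 analyses microbiological outcomes with methods similar to those for the primary endpoint. It also allows general correlations between measurements and adjustment for unspecified subject characteristics.

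No section defines a sil/16S ratio, a delta-Ct, load as a covariate for the resistance outcome, a detection limit for sil, or a rule for a negative sil result in a low-load sample.

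**The concern.** The number of sil copies in a reaction is the number of bacteria present multiplied by the share that carry the gene. A positive/negative call, a sil Ct per sample and sil copies per gram of tissue all move with that product. Dividing by tissue mass adjusts for the amount of tissue, not the number of bacteria. The PicoGreen quantity check measures total DNA, which does not give the resistant share either.

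This matters because a difference in load is what the trial is looking for. Section 2 explains the study dressing's action as physical binding and removal of bacteria, which lowers load, and change in load is the primary outcome. If it works as described, the molecular resistance result can shift in the same direction with no change in the resistant share. The plan could not then separate the two effects that its Rationale names. Because the gene result also leads into phenotypic testing, the same dependence could carry over there. Section 7 says the pilot is meant to supply effect estimates for later trials, and an estimate that mixes load with resistant share would be hard to use for that.

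**Working it through.** The documents give no prevalence, detection limit or effect size for silver resistance, so there is no stated figure to reproduce. The check is one identity followed by illustrations with assumed inputs.

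**1. Identity.** Let L be bacteria per gram, f the share carrying the gene and k a constant (tissue per reaction, copies per cell). Then log10(sil) = log10 L + log10 f + k. The 16S signal is log10 L plus its own constant. The difference, log10(sil/16S), is log10 f plus a constant, and L drops out.

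**2. Sil read by Ct.** At 100% PCR efficiency (assumed), one log10 fall in template raises Ct by log(10)/log(2) = 3.32 cycles. With f unchanged, a 1-log fall in load raises sil Ct by 3.32 and 16S Ct by 3.32. Sil Ct alone therefore suggests less resistance, while delta-Ct changes by 0 as long as sil stays detectable.

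**3. Sil read as present/absent, fixed share.** Assumed: 1 mg tissue-equivalent per reaction, one copy per carrier cell, Poisson sampling. P(detect) = 1 − exp(−L × 0.001 × f). Only the 10^5/g level has a source in the documents (the high-burden threshold in Section 2 and Appendix A).

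| Share f | 10^6/g | 10^5/g | 10^4/g |
|---|---|---|---|
| 10% | 100% | 100% | 63% |
| 1% | 100% | 63% | 10% |
| 0.1% | 63% | 10% | 1% |

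For example, f = 1% and L = 10^5/g gives 1 − exp(−1) = 63%.

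**4. Sil read as present/absent, varying share.** Assumed: log10 L ~ N(6, 1) and log10 f ~ N(−3, 1), independent, with f unaffected by treatment. Their sum is N(3, √2). With detection limit 10^q copies/g and load fall d, P(sil+) = 1 − Φ((q − 3 + d)/√2).

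| Limit (copies/g) | No fall | 1-log fall | 2-log fall |
|---|---|---|---|
| 10^2 | 76% | 50% | 24% |
| 10^3 | 50% | 24% | 8% |
| 10^4 | 24% | 8% | 2% |

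The spurious difference is 16 to 26 points for a 1-log larger fall in one arm and 22 to 52 points for a 2-log larger fall. With 15 per arm, a normal-approximation test of two proportions would reach two-sided p < 0.05 in about 22–31% and 44–85% of trials respectively. That approximation is rough at these counts.

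**5. Replicates.** Appendix A runs all qPCR in triplicate. If sil is run that way and any positive replicate counts, 63% becomes 1 − (1 − 0.632)^3 = 95% and 10% becomes 1 − (1 − 0.095)^3 = 26%. The drop between those two loads is still large.

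**The case against.** The plan offers more than a gel screen, and several stronger readings go beyond it.

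- **A reader might infer that the genes are only scored present or absent.** The reporting section plans Ct for the silver resistance genes. The fair criticism is that the two subsections disagree on the read-out and that neither version is normalised.
- **A reader might infer that resistance is never related to load.** Gene results are to be reported with a corresponding CFU/g, 16S is measured on the same samples, raw qPCR data go to the sponsor, and Section 7 allows general correlations. If sil is read by Ct, the ratio could be formed later. What is missing is its prespecification.
- **A reader might infer that a load-lowering dressing will look as if it reduces resistance.** That needs a between-arm difference in load change and, for yes/no calls, sil copies near the detection limit. At a 10% share, detection is about 100% at both 10^6 and 10^5/g. Section 4.2 selects ulcers already treated with silver, so low shares are not clearly the relevant ones.
- **A reader might call the comparison confounded.** Load is measured after randomisation. The comparison of absolute sil detection between arms is valid for its own question, namely how much resistant burden remains. For a dressing meant to remove bacteria, that question has meaning.

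The phenotypic work also classifies individual isolates by MIC, so it does not depend on total gene quantity in the same way, although no denominator for a resistant proportion is given.

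These points limit the claim but do not remove it. The absolute measure answers a different question from the resistant share, and nothing in the plan says which is meant or supplies the second.

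**Conclusion.** The concern holds in a limited form. Appendix A must say whether sil is an end-point or a quantitative assay. Under either reading, the molecular resistance outcome reflects load as well as the share of bacteria carrying the gene. If load falls more in one arm, the result may be taken as less silver resistance with no change in that share.

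The direction follows from the identity and needs no assumed prevalence. The size does rest on assumptions. It ranges from almost nothing when sil copies are plentiful to 16–26 points of apparent positivity per 1-log difference in load under the varying-share model. The documents do not support saying that the artefact will occur, or that the randomised comparison of absolute sil is invalid.

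This affects a secondary outcome in an exploratory pilot sized without a power calculation, and it leaves the primary analysis untouched. It is worth correcting because the correction is cheap and uses samples and a platform already in the plan.

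**What to change.** In Appendix A, reconcile the detection and reporting subsections, then state the following.

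1. silE, silP and silS are read by qPCR on the same DNA extracts as 16S. Gel sizing and sequencing confirm product identity.
2. The measure of **resistant share** is sil relative to 16S (log10 sil/16S or delta-Ct), per gene, as change from T0.
3. The measure of **resistant burden** is absolute sil detection and sil copies per gram, reported beside the ratio.
4. Undetected sil is left-censored at the smallest share detectable given that sample's 16S count. Under the 1 mg assumption, 10^4/g puts 10 bacteria in a reaction, so even single-copy detection cannot see a share below 1/10 = 10%. At 10^6/g there are 1,000 bacteria and the limit is 0.1%. Because a change from T0 cannot be calculated directly when either value is censored, fit T0, T2 and T3 in a model that accepts a separate censoring limit for each sample.
5. The ratio is not an exact resistant share. Appendix A itself recognises that rDNA copy number varies, so a shift in species mix can move the ratio.

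The cost is appendix wording plus standard curves for three genes, or a check that the assays' efficiencies are close enough for delta-Ct. No new samples or visits are needed. The downside is that low-load negatives become uninformative instead of counting as resistance-free, which reduces the usable information in a small trial.
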